## **I. Administrative information:**

### **1. Title:**

Clinical Evaluation of Low-shrinkage Giomer Resin Composite versus Resin-Modified Glass ionomer in Treatment of Cervical Caries Lesions: A Randomized Clinical Trial

### **2. Protocol Registration:**

The study is registered on [www.clinicaltrials.gov](http://www.clinicaltrials.gov) under ID NCT05930548.

### **3. Protocol version:**

This is the second version of the protocol (July - 2023).

### **4. Funding:**

This study is self-funded research by the main researcher.

### **e) Role of study sponsor and funders**

The principal investigator will fund the trial and all the materials required for the research. Funding will be sought and attempted upon approval of protocol.

**f) Role of steering committee**

**Scientific committee of the Department of Conservative Dentistry**

- Ensuring that the research idea follows the research plan of the department.
- Approve the protocol and the research after being reviewed by the evidence-based dentistry committee and ethical committees.
- Picots revision.
- Protocol revision.
- Approving the methodology.
- E-mail: [contact]

**Medical Biostatistics Unit (MBU), Faculty of Dentistry, Cairo University:**

- Sample size revision.
- E-mail: [contact]

**Ethical Committee, Faculty of Dentistry, Cairo University**

- Responsible for ensuring that the trial does not violate participant's privacy.
- Undertake review free from bias and influence.
- Provide advice to the researchers on all aspects of welfare and safety of research participants.
- Protect dignity, rights, and well-being of the potential research participants.
- Approval of informed consent form.
- E-mail: [contact]

**g) Faculty and University board:**

Protocol approval following departmental approval.

## **II. Introduction**

### **A) Background and Rationale:**

#### **6.a)**

##### **Research Question:**

In patients with cervical caries lesions, will low-shrinkage giomer resin composite have similar clinical performance as resin-modified glass ionomer?

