## **B) Study Objectives:**

### **7. Aim of the study:**

This study is conducted to evaluate the clinical performance of low-shrinkage giomer resin composite versus resin-modified glass ionomer in restoration of cervical caries lesions, using both Modified USPHS and Revised FDI criteria.

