### **Hypothesis:**

This study will be designed to test the null hypothesis that the low-shrinkage giomer resin composite will have the same clinical performance as resin-modified glass ionomer in cervical restorations, using both Modified USPHS and Revised FDI criteria.

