## **C) Trial Design**

- Study design: Randomized clinical trial (parallel group, two arm study).
- Triple-blinded (participants, outcome assessors and statisticians).
- Allocation ratio; 1:1
- Framework: Superiority frame.

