### 14. Sample size calculation:

The sample size was calculated based on a previous study by *Vural et al in 2021*, in which percentage of successful class V restorations (Score A and B) using resin modified glass ionomer regarding marginal discoloration was 68.7%. By implementing a two tailed Z test for difference between two independent proportions with an alpha level of 5% and a power of 80%. The minimum sample size needed was 23 per group in order to detect a difference of 30%. Sample size was increased by 20% to compensate for possible dropouts to reach 28 teeth per group. Sample size was performed using G\*Power version 3.1.9.2 for windows.

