### **20. Statistical analysis plan:**

#### **a) Statistical Methods:**

Data will be analyzed using Medcalc software, version 19 for windows (MedCalc Software Ltd, Ostend, Belgium). Categorical data will be described as frequency and percentage. Intergroup comparisons between categorical variables will be performed using the chi square test, while intragroup comparisons within each intervention will be performed using Cochran's Q test followed by pairwise multiple comparisons. A p-value less than or equal to 0.05 will be considered statistically significant and all tests will be two tailed. The statistical power of the study will be set at 80 % with 95 % confidence level.

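### The research question asks whether giomer performs similarly to RMGI, but the plan is a superiority design with no margin and no confidence interval for the difference, so only a non-significant p-value could supply a yes

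*Combined protocol and SAP*

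**What the plan says.** In the combined protocol and SAP, the Research Question (section 6.a) asks "will low-shrinkage giomer resin composite have similar clinical performance as resin-modified glass ionomer".

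The design sections are built to detect a difference:

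- **Aim (section 7):** neutral, to "evaluate the clinical performance of low-shrinkage giomer resin composite versus resin-modified glass ionomer in restoration of cervical caries lesions".
- **Hypothesis:** a "null hypothesis that the low-shrinkage giomer resin composite will have the same clinical performance as resin-modified glass ionomer in cervical restorations".
- **Trial Design (C):** "Framework: Superiority frame".
- **Sample size (section 14):** a "two tailed Z test for difference between two independent proportions with an alpha level of 5% and a power of 80" per cent, with 23 per group "in order to detect a difference of 30" per cent, raised to 28 teeth per group for dropout.
- **Statistical Methods (section 20.a):** "Intergroup comparisons between categorical variables will be performed using the chi square test". The decision rule is "A p-value less than or equal to 0.05 will be considered statistically significant and all tests will be two tailed".

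No section gives an equivalence or non-inferiority margin. Section 20.a plans frequencies, percentages and p-values. Its one mention of a 95% confidence level belongs to the power statement and does not commit to an interval for the difference between groups.

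**The concern.** A two-sided test of a no-difference null can answer that the materials differ. It cannot answer that they are similar. If p is at or below 0.05, the design works as intended. If p is above 0.05, the plan has no rule that separates similar from not shown to differ, and the question as worded invites the first reading. With 23 to 28 teeth per group, two non-significant results can mean quite different things: one may exclude the 30-point difference the trial was sized for, while the other does not. The p-value does not show which case applies. An interval for the difference does, and none is planned.

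**Working it through.** **Inputs.** From section 14: RMGI success 68.7% (marginal discoloration only), difference 30 points, two-sided 5%, power 80%, 23 per group, 28 after dropout. Assumptions: success rates of 80% and 90% as a range, giomer 20 points worse, equivalence margins of 20 and 30 points, independent teeth, and an uncorrected chi-square test on a binary success outcome.

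**1. The plan's own figure.** The direction of the 30 points is not stated. Taking 68.7% against 98.7%, the mean is 83.7%, and with pooled variance under the null:

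n = [1.96·√(2·0.837·0.163) + 0.8416·√(0.687·0.313 + 0.987·0.013)]² / 0.30² = (1.024 + 0.402)² / 0.09 = 22.6, so 23.

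Then 23 × 1.2 = 27.6, so 28. Both stated figures reproduce, which confirms sizing to detect a difference. A fall to 38.7% would need 43 per group.

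**2. Precision at equal rates.** Approximate 95% half-width = 1.96·√(2p(1−p)/n). For example, at 68.7% and n = 23: 1.96·√(2·0.687·0.313/23) = 0.268.

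| Success in both groups | n = 23 | n = 28 |
|---|---|---|
| 68.7% (protocol) | 26.8 points | 24.3 points |
| 80% (assumed) | 23.1 | 21.0 |
| 90% (assumed) | 17.3 | 15.7 |

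**3. How often a non-significant result still reaches 30 points.** Every pair of counts was enumerated with exact binomial probabilities at equal true rates. Pairs with p > 0.05 were kept, and the share whose Newcombe 95% interval reaches −30 or +30 points was computed.

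| Success in both groups | n = 23 | n = 28 |
|---|---|---|
| 68.7% | 68% | 51% |
| 80% (assumed) | 50% | 35% |
| 90% (assumed) | 20% | 9% |

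**4. Two results the p-value does not separate.** RMGI 19/28 against giomer 22/28: p = 0.37, interval −12 to +32 points. RMGI 19/28 against giomer 21/28: p = 0.55, interval −16 to +29 points. Both are non-significant, but only the second excludes 30 points. With RMGI at 19/28, giomer counts 12 to 25 are non-significant (14 results), and 10 of these have intervals reaching 30 points. With RMGI at 16/23, counts 10 to 21 are non-significant (12 results), and 9 do.

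**5. Missing a real deficit.** With RMGI at 68.7% and giomer truly at 48.7% (20 points worse, assumed), the exact chance of a non-significant chi-square result is 71% (n = 23) or 68% (n = 28).

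**6. Could the planned size support similarity?** Exact power at 28 per group to place the Newcombe 90% interval inside the margin, with equal true rates:

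| Success in both groups | 30-point margin | 20-point margin |
|---|---|---|
| 68.7% | 62% | 8% |
| 90% (assumed) | 95% | 49% |

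The answer depends on the true rate and on a margin the documents do not give.

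**The case against.** The strongest reply is that this is one word in an introductory question. It can be read as a lay restatement of the null hypothesis, while the framework statement governs and agrees with the sample size and the test. That is fair, and the design itself is not faulted. A second reply is that the planned frequencies would let a reader compute an interval. That holds only for an outcome reduced to success or failure. It also leaves the interpretation to the reader after the result is known.

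The size of the problem is also open to challenge. The figure of 68.7% concerns marginal discoloration alone, and the reference list describes its source as a 36-month split-mouth trial, whereas this trial is parallel-group and ends at 12 months. At higher success rates the intervals are narrower and the problem smaller. This stands, so the results are given as a range.

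A reader might infer four stronger things that the documents do not support:

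- **That the protocol will read non-significance as similarity.** No section says so.
- **That superiority is the wrong framework, or that the trial must be re-sized.** The null, framework, sample size and test are mutually consistent and valid for detecting a difference.
- **That every non-significant result is compatible with 30 points.** Step 4 shows some are not.
- **That the trial is too small for any similarity claim.** Step 6 shows this turns on the rate and the margin.

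**Conclusion.** The concern holds as a mismatch between the question and the plan, together with a missing interval. As written, a yes to the research question could come only from p above 0.05, and that would be weak evidence. How weak varies: across success rates from 68.7% to an assumed 90%, between 68% and 20% of non-significant results at 23 per group, and between 51% and 9% at 28 per group, would still be compatible with the difference the trial was sized to detect. These figures assume equal true rates and a binary outcome, whereas the primary outcome is an ordinal FDI score. The absence of a margin and of a planned interval rests on none of these assumptions. A significant result would be unaffected. This is a cheap improvement; the trial's validity is not in question.

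**What to change.** 1. Reword the Research Question (section 6.a) to match the two-sided design, for example: *Does low-shrinkage giomer differ from RMGI in clinical performance?*

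2. Add to Statistical Methods (section 20.a): *The difference between groups in the 12-month proportion of successful restorations will be reported with its 95% confidence interval (Newcombe or Miettinen-Nurminen). A p-value above 0.05 alone will not be reported as similarity or equivalence; the result will be interpreted from the interval.*

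3. Before analysis, fix one definition of success on the FDI scores and state which property or composite it uses. Reconcile it with section 12, where the cost-per-success text defines success both as absence of failure at 12 months and as a clinically excellent rating at 12 months, and the ICER uses the latter.

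**Cost.** No patients are added, and the randomisation and the chi-square test stay as they are. The sponsor gives up a similarity claim based on non-significance and must settle one success definition, which takes some thought because the outcome is ordinal and covers several properties. If the chi-square test is run on more than two score categories, its p-value and the interval describe different contrasts and may disagree.

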##### **Statement of the problem:**

Management of cervical lesions presents serious problems with any restorative material. The two most common reasons for restoration failure are secondary caries at the tooth-restoration interface and loss of retention (*AlQranei et al, 2021*). Class V lesions often exhibit a low retentive cavity configuration (C-factor); which is responsible for marginal gaps around the restorations (*AL-Gailani et al, 2019*). Cervical margins -lying in either dentin or cementum- show unfavorable bonding performance (*Kim et al, 2017*), besides being usually subgingival where moisture control is difficult (*Zhang et al, 2021*). The subgingival margin is not clinically desirable due to difficulty in cleaning and increased biofilm accumulation (*AlQranei et al, 2021*). Therefore, the selection of the restorative material can be challenging.

Resin composites are known for their high mechanical properties, excellent esthetic properties, and ease of clinical application. However, when compared with glass ionomers, resin composite has no cariostatic effect on tooth structure (*Tonprasong et al, 2021*). In addition, microleakage caused by polymerization shrinkage of resin composite leads to plaque accumulation and secondary caries (*Huang et al, 2021*). On the other hand, resin-modified glass ionomer has many advantages, yet still it has lower weakness and esthetic properties compared to resin composite (*AlQranei et al, 2021*).

##### **Rationale for carrying out the trial:**

Many factors may impede the ability to achieve optimum cervical restorations with perfect marginal seal and long-term success (*AlQranei et al, 2021*). In high caries-risk patients, restoring class V caries lesions requires a material with high mechanical, esthetic, and biological properties.

Resin-modified glass ionomer bonds chemically to tooth structure, and releases fluoride, but has poor esthetic and wear resistance properties. Resin composite has enhanced esthetic properties, but show high failure rates due to marginal discoloration, secondary

caries because of polymerization shrinkage (*Toz-Akalin et al, 2023*). Low-shrinkage giomer resin composite has been developed to deal with such defects. However more investigations are needed to compare between resin-modified glass ionomer and giomer low-shrinkage resin composite regarding microleakage and secondary caries in cervical carious lesions (*AL-Gailani et al, 2019*).

Surface reaction PRG (S-PRG, known as giomer resin composite) is formed using fluoro-boro-aluminaosilicate glass. The surface layer of the glass filler is coated with a porous inorganic silica glass layer “surface-modified layer” through the sol-gel method. Then, polyacrylic acid is sprayed on the fillers leading to formation of glass ionomer phase. This glass ionomer phase is located between the surface modified layer and the surface of fluoro-boro-aluminaosilicate glass core, giving a tri-laminar structure. Such unique structure gives giomer resin composites the capability to release six key ions which are fluoride, aluminum, borate, silicate, strontium, and sodium ions. These ions exhibit acid neutralizing ability and help to prevent demineralization of enamel and dentin, reducing the possibility of secondary caries (*Toz-Akalin et al, 2023*).

Giomers have other advantages such as low volumetric shrinkage and hence low polymerization shrinkage stresses. Thus, they can be used in areas where bonding to dentin is poor as the gingival margin in cervical lesions (*AL-Gailani et al, 2019*). The most remarkable feature of the low-shrinkage giomer resin composite is its unique shrinkage of 0.85 percent by volume. Such remarkable feature is due to the novel SRS (Steric Repulsion Structured) molecule which is designed to decrease polymerization shrinkage through molecular steric repulsion resulting in a stable restoration microstructure (*AlQranei et al, 2021*). Thus, it is claimed to help prevent marginal leakage, secondary caries, marginal discoloration, and postoperative sensitivity. Its main benefits are low volumetric shrinkage, chameleon effect, easy to handle, and sustained fluoride release and can be recharged due to the integrated S-PRG filler technology (*Toz-Akalin et al, 2023*).

However more investigations are needed to compare between resin-modified glass ionomer and low-shrinkage giomer resin composite regarding microleakage and secondary caries in cervical carious lesions (*AL-Gailani et al, 2019*).

### **Review of literature:**

The development of cervical lesions in permanent dentition may be related to carious or non-carious origin. Class V caries lesions may occur due to different factors

such as poor oral hygiene, dietary habits, or xerostomia (*Akarsu et al, 2021*).

Management of cervical lesions presents serious problems with any restorative material. The two most common reasons for restoration failure are secondary caries at the tooth-restoration interface and loss of retention (*AlQranei et al, 2021*). Class V lesions often exhibit a low retentive cavity configuration (C-factor); which is responsible for marginal gaps around the restorations (*AL-Gailani et al, 2019*). Cervical margins -lying in either dentin or cementum- show unfavorable bonding performance (*Kim et al, 2017*), besides being usually subgingival where moisture control is difficult (*Zhang et al, 2021*). The subgingival margin is not clinically desirable due to difficulty in cleaning and increased biofilm accumulation (*AlQranei et al, 2021*). Therefore, the selection of the restorative material can be challenging.

In this context, fluoride containing adhesive materials are considered ideal in restoring class V carious lesions. Resin modified glass ionomers (RMGI) are highly recommended in the restoration of cervical lesions. The most important advantages of glass ionomer are its chemical adhesion to the tooth structure, and its fluoride release (*Toz-Akalin et al, 2023*). However, RMGI has lower weakness and esthetic properties compared to resin composite (*AlQranei et al, 2021*).

Resin composites have been widely used in dental practice; because of their high mechanical properties, excellent esthetic properties, and ease of clinical application. However, when compared with glass ionomers, resin composite has no cariostatic effect on tooth structure (*Tonprasong et al, 2021*). In addition, polymerization shrinkage of resin composite is of major concern; where mechanical stresses are developed due to contraction leading to break the marginal seal between resin composite and tooth structure. Polymerization shrinkage can cause clinical issues such as restoration or tooth fracture, bond degradation and solubility, and microleakage (*Algailani et al, 2022*). The microleakage caused by polymerization shrinkage of resin composite leads to plaque accumulation and secondary caries (*Huang et al, 2021*). Thus, choosing a fluoride-releasing and low-shrinkage resin composite may play a critical role in success of cervical restorations (*AL-Gailani et al, 2019*).

The continued development of resin composites has led to the introduction of Giomer technology. By combining the characteristics of resin composite and glass ionomer, hybrid products called giomers have been obtained. Giomer resin composite

offers protection against caries, along with improved functional and esthetic properties; through incorporating particles of pre-reacted glass fillers (PRG) into the matrix of resin composite (*Rusnac et al, 2019*). The PRG-ionomer phase has the capability to release six key ions which are fluoride, aluminum, borate, silicate, strontium, and sodium ions. These ions exhibit acid neutralizing ability and help prevent demineralization of enamel and dentin, leading to decrease the possible incidence of secondary caries (*Toz-Akalin et al, 2023*). This PRG technology provides giomer with both fluoride release and recharge, similar to glass ionomer while still maintaining the original physical properties of resin composite (*Bheda et al, 2020*).

Beautifil™ II LS (Low shrinkage) giomer resin composite (Shofu Inc, Kyoto, Japan) shows both sustained fluoride release and recharge, and low volumetric shrinkage of less than 1% with low resultant polymerization shrinkage stress. Such remarkable feature is due to the novel SRS (Steric Repulsion Structured) molecule which is designed to decrease polymerization shrinkage through molecular steric repulsion resulting in a stable restoration microstructure (*AlQranei et al, 2021*). Thus, low shrinkage giomers are best indicated in class V cavities where the dentin bonding agent does not have high strength (*Algailani et al, 2022*).

A recent clinical trial compared the clinical performance of giomers versus resin modified glass ionomer in proximal lesions. Marginal adaptation was higher in giomers than resin-modified glass ionomers after 12 months (*Inthihas et al, 2019*). Also, a systematic review investigated in vivo longevity of giomers compared to other adhesive restorative materials (hybrid resin composite, compomer, and RMGIC), and concluded that RMGIC was the most successful material in terms of biological properties while giomers had the longest survival rate (*Bheda et al, 2020*). An in-vitro study evaluated the surface roughness and fluoride release of Beautifil II and Fuji II LC (resin-modified glass ionomer). Resin-modified glass ionomer showed the highest fluoride release, while the giomer showed an intact, smooth surface with no irregularities as those found in glass ionomer. Thus, the smooth surface of giomers inhibit biofilm formation, decreasing the risk of dental caries and periodontal diseases (*Komalsingsakul et al, 2022*). Regarding the mechanical properties of giomers, it has exhibited a higher flexural strength value when compared to glass ionomer cements. The hardness values were twice as high for the giomer when compared to self-curing and light-curing glass ionomer cements (*da Silva et al, 2021*).

### **6.b) Choice of comparators:**

In our study, the comparator material will be light cured resin modified glass ionomer restorative. RMGI is recommended to restore carious cervical lesions; especially with its ability to inhibit secondary caries due to its fluoride releasing ability. The main advantage of RMGI is its capability to chemically bond to tooth structure, even in the presence of moist dentin. RMGI reaction can be achieved by both acid-base reaction (induced by glass ionomer component) and polymerization reaction (induced by resin component). Thus, RMGI has better mechanical properties, wear resistance, and improved esthetics compared with conventional glass ionomer (*AlQranei et al, 2021*). In addition, the coefficient of thermal expansion of glass ionomer which is similar to that of tooth structure, allows for proper marginal adaptation without marginal leakage (*Bollu et al, 2016*).

